Patient data collected	
The following information will be recorded in an electronic Case Report Form (eCRF) using the data available in the medical file or collected during the visit (as part of the routine patient management):
 
 » Date of the inclusion visit (the only study visit) and type of visit (outpatient visit, day hospital, in-patient hospitalisation). » Patient eligibility criteria. » Demographic data: year of birth, gender, smoking status » Clinical data: height, weight, medical history, comorbidities related to GCs » GCA patient journey: Incident or prevalent patient (threshold: 6 weeks before visit), date of initial diagnosis, date of GCA signs/symptoms, physician(s) who referred the patient. » GCA characteristics: Initial presentation (cranial, polymyalgia rheumatica, extracranial, ESR/CRP, general signs), diagnosis methods, clinical form (relapsing, GCs-dependence, with GCA complications), GCA activity (clinical signs and symptoms) » Treatments: previous and on-going specific GCA treatments since diagnosis (GCs, immunosuppressants, targeted biologic therapy, Janus kinase inhibitors), treatments at diagnosis and inclusion visit, treatments for comorbidities related to GC intake. 
Four paper questionnaires (SF-36, EQ5D, FACIT-fatigue, global arteritis activity VAS) will be completed by the patient and one by the physician (global arteritis activity VAS). All questionnaires will be returned in the pre-paid reply envelope to the CRO in charge of the data entry.
 
No safety data will be collected. Physicians will report adverse event as per usual French process, if appropriate.
 
The use of indirectly personally identifiable data is crucial in this study since it will allow quality control. Physicians may be requested written corrections for missing or inconsistent data essential to the study. Patient identity will be coded in the eCRF and the questionnaires. The patients will be identified using a number made up of 4 digits: 3 digits for the investigator and 1 digit for the inclusion order number. The physician will maintain a patient identification table with patient's identity and corresponding study number. This table will be stored by the

	
physician in a secure manner and no one else will have access to it. At the end of the study, the physician will be responsible for destroying this table.

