Start date for all signs and symptoms (month, year)

- Diagnostic methods: TAB, High-resolution color Doppler ultrasound of the temporal arteries, MRI of the temporal arteries, 18FDG-PET, Computed tomography

angiography (CTA), Magnetic resonance angiography, signs/symptoms, erythrocyte Sedimentation Rate (ESR), C-Reactive protein (CRP), other.

○ Clinical form:

- Relapses: date (month, year), treatments and doses, criteria for identifying relapse (clinical, biological, other)
- GCs-dependence: dose of prednisone after GCA diagnosis
- Complications during the course of the disease: ischemia-related vision loss, stroke, TIA, thoracic or abdominal aortic aneurysm, other.

» GCA activity:

- Clinical signs and symptoms of GCA activity at diagnosis and at inclusion: GCA-related fever ($> 38^{\circ}\text{C}$), symptoms of PMR (morning stiffness and/or pain in the shoulder and/or pelvic girdles, inflammatory arthromyalgia, peripheral arthritis, other), localised headache, temporal artery or scalp tenderness, visual signs or symptoms (e.g. acute or subacute vision loss due to arteritic anterior ischemic optic neuropathy; A-AION), transient blurry vision (generally monocular or at least affecting one eye at a time, but potentially affecting both eyes), jaw or mouth pain, extremity claudication, other features judged by the investigator to be consistent with a GCA or PMR flare.

Start date of signs and symptoms (month, year)

» Treatments:

- Previous and on-going specific GCA treatments since diagnosis:
- GCs (start and end date, dose/day, administration route, current dose, cumulative dose, kinetic)
 - Immunosuppressants (MTX, cyclophosphamide, cyclosporine, azathioprine, mycophenolate mofetil, leflunomide, dapsone, hydroxychloroquine, other) (start and end date, dose at starting date, current dose, maximum dose)
 - Targeted biologic therapy (adalimumab, etanercept, abatacept, tocilizumab, infliximab, other) (start and end date, dose at starting date, current dose)
 - Janus Kinase inhibitors (start and end date, dose at starting date, current dose)
- Treatments at diagnosis and inclusion visit: antiplatelet agents, statins, antiosteoporotic treatments, antihypertensive (start date, treatment name).
- Other significant concomitant treatments (start and end date, indication)

- Treatments for comorbidities related to GC intake (start and end date, indication)

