 - If yes, contributing to diagnosis (Yes/ No/ intermediate)
- Magnetic resonance angiography done (Yes/ No)
 - If yes, contributing to diagnosis (Yes/ No/ intermediate)
- Other (Yes/No/ intermediate)

A listing of other methods will be presented.

Only diagnostic methods done in the previous month of date of diagnosis, the current month of the day of diagnosis and the month following the date of diagnosis will be considered. The diagnostic methods will be described overall, by time between first medical events related to GCA and diagnosis (qualitative variable), and by type of physicians who follows the patient.

- Previous and ongoing specific GCA treatments since diagnosis other than GCs
 - Number of patients who has taken at least one immunosuppressant since diagnosis and stopped before inclusion and the frequency of each type (Methotrexate, Cyclophosphamide, Cyclosporine, Azathioprine, Mycophenolate Mofetil, Leflunomide, Other) and duration of each treatment taken (months), ([APPENDIX](#))
 - Number of patients with at least one immunosuppressant ongoing at inclusion and frequency of each type (Methotrexate, Cyclophosphamide, Cyclosporine, Azathioprine, Mycophenolate Mofetil, Leflunomide, Other), dose at the initiation (mg), maximal dose (mg), current dose (mg) and duration of each treatment taken (months).([APPENDIX](#))
 - Number of patients who has taken at least one targeted biological therapy since diagnosis and stopped before inclusion and the frequency of each type (Adalimumab, Etanercept, Abatacept, Tocilizumab, Infliximab, Other) dose at the initiation (mg) and duration of each treatment taken (months) ([APPENDIX](#))
 - Number of patients with at least one targeted biological therapy ongoing at inclusion and the frequency of each type (Adalimumab, Etanercept, Abatacept, Tocilizumab, Infliximab, Other) dose at the initiation current dose and duration of each treatment taken (months) ([APPENDIX](#))
 - Number of patients who has taken at least one other long-term treatment for the medical care of GCA since diagnosis and stopped before inclusion and the frequency of each type (Baricitinib, Dapsone, Hydroxychloroquine, Tofacitinib, Other), dose at the initiation, maximal dose and duration of each treatment taken (months) ([APPENDIX](#))

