- Proportion of patients with at least one general sign at diagnosis and the proportion of each sign (fever $>$ 38°C with no other etiology than GCA, weight loss and its value (%), alteration of the general condition)

For the value of ESR and CRP at diagnosis, only value measured in the previous month, the current month and the month following the date of diagnosis will be considered. For values at inclusion, only measures done within 6 month before the date of inclusion will be considered.

A listing of other initial characteristics related to GCA at diagnosis will be presented.

- Clinical form:
 - Proportion of patients with at least one relapse
 - In patient with at least one relapse:
 - Number of relapses per patient
 - Time between first relapse and diagnosis (months) ([APPENDIX](#))
 - Mean time between 2 consecutive relapses (months) ([APPENDIX](#))
 - The following information will be summarized by relapse:
 - Proportion of used criteria to assess relapse (Clinical/ Biological/ Imagery/ Other)
 - Proportion of patients using GCs just before the relapse
 - GCs dose at relapse diagnosis (mg/day)
 - Proportion of relapses of patients with Immunosuppressants just before the relapse
 - Proportion of relapses of patients with Targeted biologic therapy just before the relapse
 - Proportion of relapses of patients using other treatments just before the relapse
 - Proportion of relapses for which Glucocorticoids (GCs) were used as medical care for the relapse
 - GCs dose used for relapse medical care (mg/day)
 - Proportion of relapses for which Immunosuppressants were used as medical care for the relapse
 - Proportion of relapses for which Targeted biologic were used as medical care for relapse
 - Proportion of relapses for which other GCA (HORTON) treatments were used as medical care for relapse.
 - Distribution of GCs dependence
 - Current dose at inclusion (mg/day)
 - Number of kinetics per patient since diagnosis
 - Time between first kinetic and diagnosis (months) ([APPENDIX](#))
 - Proportion of patients with at least one kinetic ongoing at inclusion
 - Mean time between 2 consecutive kinetics (months) ([APPENDIX](#))
 - Total cumulative GCs dose according to investigator (excluding IV bolus) since diagnosis (mg) ([APPENDIX](#))
 - The following information will be summarized by Kinetic:
 - Kinetic duration (months) ([APPENDIX](#))
 - Proportion of kinetics with IV initial administration (bolus) (Yes/No)
 - If yes, total number of days

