 - IV bolus dose (mg)
 - Switch PO dose (mg/day)
 - Cumulative dose according to investigator (mg)
 - Proportion of kinetics for which a corticotherapy for GCA (Horton) care has restarted after the kinetic
 - Proportion of patients with at least one GCA complication
 - Proportion of patients with ongoing specific treatment(s) for GCA complications

Current and/or past GCA complications according to the investigator judgment will be coded using the medical dictionary MedDRA®. They will be described by SOC and PT overall and by type of physicians who follows the patient.

To determine the potential factors associated to relapse, a logistic regression will be used. The outcome variable will be relapse (Yes/ No). First, a univariate analysis will be conducted. All significant

factor at the 20% threshold will be selected for a multivariate analysis. A backward elimination procedure will be used with a threshold of 5%.

The associated factors that will be studied are:

- Age (in classes)
- Gender (Male/Female)
- BMI at diagnosis (in classes)
- Smoking status (Smoker/ Former smoker/ Non-smoker ever / Unknown)
- Type of patient (Prevalent or incident)
- Physician who referred the patient (General practitioner/ Ophthalmologist / Neurologist/ Emergency/ Internist/ Rheumatologist/Other),
- Patient considered with late diagnosis by the physician who referred him (Yes/ No)
- Patient considered with late diagnosis according to calculated time interval between the first medical events related to GCA and diagnosis : (Yes/No)
- Patient with at least one cranial GCA symptom at diagnosis (Yes/No),
- Patients with at least one PMR symptom at diagnosis (Yes/No),
- Patient with at least one extracranial GCA symptom at diagnosis (Yes/No),
- Patient with abnormal value of ESR at diagnosis (ESR>50 mm/h)
- Patient with abnormal value of CRP at diagnosis (CRP> 25 mg/L) (Yes/No),
- Patient with fever (>38°C) at diagnosis (Yes/No),
- Patient with weight loss at diagnosis (Yes/No),
- Patient with alteration of the general condition at diagnosis (Yes/No),
- Patient has taken at least one immunosuppressant since diagnosis (Yes/No)
- Patient has taken at least one targeted biological therapy since diagnosis (Yes/No)
- Patient has taken at least one other long-term treatment for the medical care of GCA since diagnosis (Yes/No)
- VAS score (global arteritis activity) by patient (>50mm/≤50mm)
- VAS score (global arteritis activity) by physician (>50mm/≤50mm)
- Cumulative dose of GCs (mg)

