5.6 Changes from protocol

Current and past treatments used for comorbidities related to GCs will not be described as mentioned in the protocol regarding to the modifications of the CRF from version 1.2 to version 3.0 according to sponsor's decision. Indeed the dedicated table for specific treatments for comorbidities related to GCs was deleted.

This listing will include all treatments taken by patients with comorbidities related/aggravated by the use of glucocorticoids according to investigator's judgment.

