8 STATISTICAL APPENDICES

APPENDIX (Derived data)

The following derived data will be calculated and included in the listings:

(1) **Enrollment duration**

Enrollment duration (days) = date of inclusion of the last patient – date of inclusion of the first patient

(2) **Time between first medical events related to GCA and diagnosis**

For prevalent patients (not newly diagnosed):

Time between first medical events related to GCA and diagnosis (months) = date of diagnosis – date of first medical events related to GCA

For incident patient (newly diagnosed):

Time between first medical events related to GCA and diagnosis (months) = date of diagnosis (in MM/YY format) – date of first medical events related to GCA

The date of diagnosis which is in format (DD/MM/YYYY) will be transformed into (MM/YYYY)

(3) **Time between diagnosis and inclusion**

For prevalent patients:

Time between diagnosis and inclusion (months) = (date of inclusion – date of diagnosis)/30.4375

If the date of diagnosis in format (DD/MM/YYYY) is not completed, the diagnosis date in format (MM/YYYY) will be used and the inclusion date will be transformed into (MM/YYYY).

For incident patients:

Time between diagnosis and inclusion (months) = (date of inclusion – date of diagnosis)/30.4375

The date of diagnosis in format (DD/MM/YYYY) will be used.

(4) **Duration of treatment taken**

Duration of treatment taken (months) = End date – start date +1

if ongoing treatment at inclusion:

Duration of treatment taken = Date of inclusion – start date +1

For this calculation, the date of inclusion which is in format (DD/MM/YYYY) will be transformed into (MM/YYYY) as the start date of treatment.

(5) **Time between first relapse and diagnosis**

Time between first relapse and diagnosis (months) = date of first relapse after diagnosis – date of diagnosis.

For this calculation, the date of diagnosis (for incident patient) which is in format (DD/MM/YYYY) will be transformed into (MM/YYYY) as the date of relapse.

(6) Mean time between 2 consecutive relapses

Time between 2 consecutive relapses (months) = [date of relapse (i+1) – date of relapse (i)]/(Total number of relapses per patient-1)

(7) Time between first kinetic and diagnosis

Time between first kinetic and diagnosis (months) = date of initiation of first kinetic – date of diagnosis

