The percentages are calculated compared to filled data
STUDY : CHUGAI-ARTEMIS - Edition date: DDMMYY
Pgm : EFFICACYGCA.SAS

Listing 9 : Specification of other treatments used just before relapse (N= XX)

Patient ID	Number of relapse	Type of patient	Type of diagnosis	Physician who follows the patient	Specification of other treatments used just before relapse

STUDY : CHUGAI-ARTEMIS - Edition date: DDMMYY
Pgm : EFFICACYGCA.SAS

Listing 10 : Specification of other treatments used for the medical care of relapse (N= XX)

Patient ID	Number of relapse	Type of patient	Type of diagnosis	Physician who follows the patient	Specification of other treatments used as medical care for relapse

STUDY : CHUGAI-ARTEMIS - Edition date: DDMMYY
Pgm : EFFICACYGCA.SAS

Table 18 - Efficacy analysis – Clinical Form - Distribution of GCs dependance - Analysis population (N=XX)

Parameter	Statistics	Total (N=XX)
Current GCs dose at inclusion (mg/day)	Mean SD Median [Q1 ; Q3] [Min ; Max] Filled, n(%) Missing, n(%)	
Number of kinetics per patient since diagnosis	Mean SD Median [Q1 ; Q3] [Min ; Max] Filled, n(%) Missing, n(%)	
Time between first kinetic and diagnosis (months)	Mean SD Median [Q1 ; Q3] [Min ; Max] Filled, n(%) Missing, n(%)	
Patient with at least one kinetic ongoing at inclusion No Yes	n(%) n(%) Filled, n(%) Missing, n(%)	
Mean time between 2 consecutive kinetics (months)	Mean SD Median [Q1 ; Q3] [Min ; Max] Filled, n(%) Missing, n(%)	
Total cumulative GCs dose according to investigator (excluding IV bolus) since diagnosis (mg)	Mean SD Median [Q1 ; Q3] [Min ; Max] Filled, n(%) Missing, n(%)	

The percentages are calculated compared to filled data
STUDY : CHUGAI-ARTEMIS - Edition date: DDMMYY
Pgm : EFFICACY\GCA.SAS

Table 19 - Efficacy analysis – Clinical Form - Description of Corticotherapy (per kinetic) - Analysis population (N=XX)

Parameter	Statistics	Total (N=XX kinetics)
Kinetic duration (months)	Mean SD Median [Q1 ; Q3] [Min ; Max] Filled, n(%) Missing, n(%)	
Kinetic with IV initial administration (bolus) No Yes	n(%) n(%) Filled, n(%) Missing, n(%)	
If yes, Total number of days	Mean SD Median [Q1 ; Q3] [Min ; Max] Filled, n(%) Missing, n(%)	
IV bolus dose (mg)	Mean SD Median [Q1 ; Q3] [Min ; Max] Filled, n(%) Missing, n(%)	
Switch PO dose (mg/day)	Mean SD Median [Q1 ; Q3] [Min ; Max] Filled, n(%) Missing, n(%)	
Cumulative dose according to investigator (mg)	Mean SD Median [Q1 ; Q3] [Min ; Max] Filled, n(%) Missing, n(%)	

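### Glucocorticoids leave the primary treatment analysis without a declared change, and no table isolates the oral daily dose of the first course

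*SAP*

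**What the plan says.** The protocol synopsis (Patient data collected) lists, under treatments, "previous and on-going specific GCA treatments since diagnosis (GCs, immunosuppressants, targeted biologic therapy, Janus kinase inhibitors". Protocol 6.1 makes previous and ongoing specific GCA treatments a primary endpoint and does not exclude GCs. For GCs, protocol 5.3.1 plans to collect "GCs (start and end date, dose/day, administration route, current dose, cumulative dose, kinetic", so a daily dose is listed separately from the current dose.

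SAP 5.4 heads the matching primary analysis "Previous and ongoing specific GCA treatments since diagnosis other than GCs", and Tables 6–11 contain no GC row. SAP 5.6 records one departure from the protocol: "Current and past treatments used for comorbidities related to GCs will not be described as mentioned in the protocol". It does not mention the move of GCs.

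GCs appear in SAP 5.5.2 under clinical form. The per-kinetic items include "Proportion of kinetics with IV initial administration (bolus) (Yes/No", then the number of bolus days, the bolus dose, "Switch PO dose (mg/day" and the cumulative dose. The Table 19 shell has one column, headed "Total (N=XX kinetics", with filled and missing counts for each row. Item 7 of the SAP appendix on derived data already uses the "date of initiation of first kinetic".

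**The concern.** The protocol introduction calls high-dose GCs the mainstay of management, and it names GC doses among the items on which the earlier database study had limited data. A reader of the final report would expect to learn how GC treatment is started. As planned, the report gives GC dose at relapse, for relapse care, at inclusion and cumulatively, but never the oral daily dose of the first course.

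The nearest row is the switch dose, which can mislead in two ways. It mixes starting courses with restarts, which may use lower doses. Depending on an unstated rule, it may also describe only patients who began with an IV bolus. Someone comparing it with the 0.7–1 mg/kg/day in the protocol introduction could conclude that patients are under-dosed when the row is simply a mixture.

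**Working it through.** The plan states no figure on this point, so there is nothing to reproduce. The check is mainly textual. I read a kinetic as one GC course, since the SAP appendix gives each an initiation and a stop date.

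**Step 1: which GC dose rows exist (SAP 5.5.2 and Tables 17–19)**

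| Row | Unit | Oral daily dose of first course? |
|---|---|---|
| GC dose at relapse; dose for relapse care (Table 17) | relapse | No |
| Current dose at inclusion (Table 18) | patient | No: may already be tapered |
| Total cumulative dose (Table 18) | patient | No: not a daily dose |
| IV bolus dose (Table 19) | kinetic | No: intravenous |
| Switch PO dose (Table 19) | kinetic | Only partly: all courses together, applicability unstated |
| Cumulative dose (Table 19) | kinetic | No: not a daily dose |

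**Step 2: which kinetics the switch dose covers.** In Table 19 the if-yes condition is attached to the number of bolus days. It is not repeated for the bolus dose or the switch dose. A programmer could apply the switch row to all kinetics or only to bolus kinetics. If only bolus kinetics have a value, the missing count mixes not-applicable with truly missing.

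**Step 3: what the incident/prevalent split recovers.** SAP 5.5.2 requires the clinical-form endpoints by type of patient. Incident patients are at most 6 weeks from diagnosis, so nearly all their kinetics should be first courses. Prevalent patients stay mixed, and the planned number of incident patients is not given. The split is noted under the Table 15 shell but not under Tables 18–19. The inclusion dose of incident patients is not a starting dose either. The protocol introduction describes reductions of 10–20% every 2 weeks once tapering starts. From an assumed 50 mg/day, one reduction gives 50 × 0.9 = 45 to 50 × 0.8 = 40 mg/day, and two give 50 × 0.81 = 40.5 to 50 × 0.64 = 32 mg/day.

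**Step 4: illustration of mixing, if every kinetic contributes.** All inputs are assumed except 0.7–1 mg/kg/day. At an assumed 60 kg that is 0.7 × 60 = 42 to 1 × 60 = 60 mg/day; take 50. With m kinetics per patient and later-course dose L, the first-course share is 1/m and the combined mean is 50 × (1/m) + L × (1 − 1/m).

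| m | First-course share | L = 10 | L = 20 | L = 40 |
|---|---|---|---|---|
| 1.2 | 83% | 43.3 | 45.0 | 48.3 |
| 1.5 | 67% | 36.7 | 40.0 | 46.7 |
| 2.0 | 50% | 30.0 | 35.0 | 45.0 |

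**Step 5: illustration of restriction, if only bolus kinetics contribute.** With an assumed 10–30% of first courses begun by bolus, 0.10 × 300 = 30 to 0.30 × 300 = 90 patients have a first-course value. With an assumed SD of 15 mg/day, the 95% half-width t × 15/√n is 5.6 (n = 30), 3.1 (n = 90) or 1.7 (n = 300) mg/day. The smaller sample also describes bolus-started patients only.

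Steps 4 and 5 rest on alternative readings of the row, so their effects must not be added.

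**The case against.** The strongest reply is that nothing promised is missing. The protocol does not name starting GC dose as an endpoint: 5.3.1 lists a dose at the starting date for the other drug classes but not for GCs. It also places GC dose under clinical form, as GC dependence, so the SAP's location has a basis. SAP 5.5.2 gives GC results on the same population and by physician type, as the protocol asks for treatments. With no tests planned, moving a description from primary to secondary changes no estimate. The word switch, placed directly after the bolus rows, also warns a careful reader.

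Most of this stands, and it rules out several stronger readings that a reader might infer:
- That GCs are dropped from the study. They are relocated.
- That Table 19 has no denominator. Its column counts kinetics and each row has filled and missing counts; what is missing is the rule for which kinetics the switch dose applies to.
- That first and later courses are mixed in every result. The incident column largely separates them.
- That GCs are singled out in the shells. Tables 6–11 have no dose rows for the other drugs either, although the SAP 5.4 text asks for an initiation dose for most of those groups.

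The objection does not remove three facts: the move is undeclared, the switch row is undefined, and no row isolates the first-course oral daily dose in the overall or prevalent results.

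**Conclusion.** The point holds as a cheap improvement, not as a defect that threatens the study's conclusions. An undeclared relocation of GCs from the primary to a secondary analysis, and the absence of any row for the first-course oral daily dose, both follow directly from the text.

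The size cannot be established. Kinetics per patient, later-course dose, body weight, bolus share and SD are all assumptions. On them the combined mean could sit between about 2 (50 − 48.3 = 1.7) and 20 (50 − 30) mg/day below a first-course mean of 50. The half-widths in step 5 are set against no precision target, because protocol 7.1.1 gives none. It would be wrong to read either illustration as a predicted bias.

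**What to change.** 1. In Table 19, report the dose rows separately for first and later kinetics. No new data are needed, since the first kinetic is already identified for appendix item 7.
2. State in SAP 5.5.2 which kinetics the switch dose applies to, and restrict the row and its missing count to them.
3. If the current CRF holds the oral dose at course start, add to Table 18 a row for the initial oral GC dose of the first kinetic (mg/day), overall and by bolus yes/no. SAP 5.6 refers to CRF version 3.0, which is not among the documents, so check this first. If the CRF does not hold the dose, do not present the switch dose as the general starting dose, and say in SAP 5.6 that starting dose is not covered.
4. List in SAP 5.6 that GCs are described in 5.5.2 rather than 5.4.

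The cost is a few extra table rows, smaller numbers per column and some sentences of text, all to be settled before database lock.

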5.5.2 Description of GCA characteristics

First the following parameters will be presented:

- Time between diagnosis and inclusion will be described as quantitative variable (months) ([APPENDIX](#))
- Type of patient
 - Proportion of incident patients (newly diagnosed): patients with a diagnosis of GCA \leq 6 weeks from inclusion
 - Proportion of prevalent patients (not newly diagnosed): patients with a diagnosis of GCA $>$ 6 weeks from inclusion.

Then the following endpoints will be described overall and by type of patient (prevalent/incident), by type of diagnosis (time between the first medical events related to GCA and diagnosis to GCA as qualitative variable in 3 classes early/in standard time/late diagnosis), and by type of physicians who follows the patient.

- Initial presentation:
 - Proportion of patients with at least one cranial manifestation at diagnosis and the proportion of each symptom of this family (Headaches/ Scalp sensitivity / Anomalies of the temporal arteries (temporal artery sensitivity or decreased pulsation) / Ischemia-related vision impairment and-or loss / Mouth pain or jaw claudication during mastication / Stroke or transient ischemic attack (TIA) / Other)

Listing of Ischemia-related vision impairment / loss and other cranial manifestation at diagnosis will be presented.

- Proportion of patients with at least one PMR symptom at diagnosis and the proportion of each symptom of this family (Morning stiffness and-or pain in the shoulder girdle/ Morning stiffness and-or pains in the pelvic girdle/ Inflammatory arthromyalgia/ Peripheral arthritis/ Other)

A listing of other PMR symptom will be presented.

- Proportion of patients with at least one extracranial event (excluding PMR) at diagnosis and the proportion of each symptom of this family (Thoracic or abdominal aortic aneurysm and-or dilatation/ Aortitis and-or involvement of aortic branch(s) in imaging/ Angina and-or Myocardial infraction/ Claudication of an upper limb and-or claudication of a lower limb/ Sign of subclavian stenosis (asymmetry of pulse, blood pressure, subclavian murmur)/ Other)

A listing of other extracranial events (excluding PMR) will be presented.

- Value of ESR (mm/1st h) and CRP (mg/L) at diagnosis and at inclusion.
- Proportion of patients having abnormal value of ESR (ESR $>$ 50 mm/h)/CRP (CRP $>$ 25 mg/L) at diagnosis
- Proportion of patients having abnormal value of ESR (ESR $>$ 50 mm/h)/CRP CRP $>$ 25 mg/L) at inclusion

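### The relapse regression omits time since diagnosis and includes treatments that build up with time or follow relapse, so its odds ratios for treatment and glucocorticoid dose can depart from 1 without any true effect

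*SAP*

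**What the plan says.** Protocol 7.2.3.2 names logistic regression for factors associated with relapse and leaves the factors to the SAP. SAP 5.5.2 then specifies: "To determine the potential factors associated to relapse, a logistic regression will be used. The outcome variable will be relapse (Yes/ No"). Factors pass a univariate screen at 20% and then backward elimination at 5%. There is no offset or person-time.

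The list has 22 candidates. Those that matter here are:

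- "Patient has taken at least one immunosuppressant since diagnosis (Yes/No"), with matching flags for targeted biologics and for other long-term treatments;
- "Cumulative dose of GCs (mg"), which Appendix item 10 sums over every GC course since diagnosis;
- "VAS score (global arteritis activity) by physician" and the same score by the patient, each cut at 50 mm;
- "Type of patient (Prevalent or incident"), the only candidate related to disease duration, with its boundary at 6 weeks.

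Elsewhere the same section says "Time between diagnosis and inclusion will be described as quantitative variable (months"), and Appendix item 3 derives it: "Time between diagnosis and inclusion (months) = (date of inclusion" minus date of diagnosis), divided by 30.4375. It is not carried into the relapse model. The section also plans to report "Proportion of relapses for which Immunosuppressants were used as medical care for the relapse", with parallel lines for GCs, biologics and other treatments. SAP 5.6 (changes from protocol) does not touch this point.

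**The concern.** A patient seen five years after diagnosis has had longer to relapse, longer to be given an adjunct drug and longer to accumulate GC dose than one seen at two months. If duration is left out, these quantities become associated with each other even when none influences another. A second route works in the other direction. A drug started to treat a relapse sets its since-diagnosis flag to Yes and is then tested as a factor for that same relapse; GCs given for a relapse likewise enter the cumulative dose.

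Tables 22 and 23 are titled as the *effect* of patient characteristics on relapse and report odds ratios with p-values. A reader could conclude that immunosuppressants, biologics or higher GC exposure go with relapse in some informative way, when the result may reflect only longer disease or treatment of the relapse itself.

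**Working it through.** The plan gives no expected odds ratio or power for this model, so there is no figure to reproduce. The check asks what the specified model returns when no association exists.

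**Inputs from the documents.** 300 patients; 6-week incident/prevalent cut; 20% and 5% selection thresholds; adjunct use of 16.7% over a mean follow-up of 3.7 years (SD 2.6) and a first GC sequence of 17.2 months (SD 16.5), both from the EGB results in Protocol 1. In the EGB sentence the two treatment percentages add to 84.3 + 16.7 = 101.0, which matters little here. The EGB data end in 2015 and tocilizumab was authorised in 2017, so biologic uptake in 2018 is unknown.

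**Assumed.** Relapse risk, disease duration, share of incident patients and timing of uptake.

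**1. Hand check, prevalent patients only.** The 6-week flag is then constant and cannot help.

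- Adjunct hazard: −ln(1 − 0.167)/3.7 = 0.049 per year.
- Assume half the patients are seen at 0.5 years and half at 5 years, with a relapse hazard of 0.2 per year, independent of treatment.
- P(relapse) = 1 − exp(−0.2t): 0.095 and 0.632.
- P(adjunct) = 1 − exp(−0.049t): 0.024 and 0.219.
- Averaged cells: both 0.0703; relapse only 0.2933; adjunct only 0.0513; neither 0.5851.
- Odds ratio = (0.0703 × 0.5851)/(0.2933 × 0.0513) = 2.73, although it is exactly 1 at each time.
- Relapse hazards of 0.1 and 0.3 give 2.21 and 3.39. An assumed adjunct hazard of 0.1 per year gives 2.46, 3.07 and 3.81 for relapse hazards 0.1, 0.2 and 0.3.

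**2. Null simulation over 27 scenarios, eligibility rule not applied.** Mean duration 1.43, 2.5 or 3.7 years; 5, 15 or 30% incident; 30, 40 or 50% ever relapsed; 16.7 or 30% treated.

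| Odds ratio under no association | Crude (as Table 22) | With incident/prevalent | With continuous time |
|---|---|---|---|
| Treatment flag | 1.9–7.3 | 1.7–3.3 | 0.98–1.02 |
| Cumulative dose, per g | 1.12–1.55 | 1.11–1.39 | 1.00–1.01 |

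With mean duration 3.7 years, 15% incident, 40% relapsed and 16.7% treated, at n = 300 the null flag passes the 20% screen in 95% of runs. It reaches p < 0.05 in 85% of runs crude and 53% with the incident/prevalent term.

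**3. When the duration route weakens.** If the drug is only ever started at diagnosis, the crude odds ratio is 0.98–1.00. In a separate set of 27 scenarios at n = 300 with the incident/prevalent term, a null flag carrying the full EGB uptake was significant at 5% in 15–78% of runs. One with a fifth of that uptake was significant in 0–13%.

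**4. Applying the eligibility rule.** SAP 3.5.1.1 requires patients to be starting or receiving GCA treatment. In these simulations patients stay in if they are within the initial GC taper, have ever had an adjunct, or have been treated for relapse. The flag's odds ratio after the incident/prevalent term was about 1.4 to 6 across scenarios with and without this rule. With the rule, in prevalent patients with log time, it fell to about 0.06–0.75. The reason is selection: long after diagnosis, a never-relapsed patient is mostly still eligible because of an adjunct, which makes adjuncts look protective. A null factor fixed at diagnosis stayed at about 1.0. One that only doubles or triples adjunct uptake gave 0.63–0.99.

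**5. VAS timing.** Protocol 5.1.1 has the questionnaires completed at the single inclusion visit. Each score therefore follows every past relapse, or coincides with one still under way. This is an argument from timing, and no effect size is attached.

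**The case against.** The strongest defence is that the study is descriptive and seeks associated factors, not causes; ever-treated patients in this sample may truly have relapsed more often. That is fair, and the causal reading rests largely on one word in the table titles. But the association would still be credited to drugs or dose when it may come only from disease duration or from treating the relapse.

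The plan also has partial safeguards. Type of patient is a candidate, and Tables 16 and 17 describe relapse timing and the treatment before and for relapse. These do not correct Tables 22 and 23. Every patient beyond 6 weeks forms one class, the flag can drop out at either selection step, and the univariate odds ratios are unadjusted.

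It can fairly be said that the sizes rest on assumptions and range widely. That stands: the mechanism is firm, the numbers are illustrative.

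Four stronger readings are tempting and not supported:

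- *Adding time since diagnosis would make the treatment flags valid.* The return to 1 in step 2 ignores the eligibility rule; with that rule the time-adjusted odds ratio can fall well below 1, and reverse causation remains in any case.
- *Every factor in the table is distorted.* Factors fixed at diagnosis and unrelated to duration are not inflated by this route.
- *The model must be confined to prevalent patients.* Nothing shows that this is necessary.
- *The VAS always comes after relapse.* It may be concurrent.

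**Conclusion.** The point holds and should be fixed. As specified, the model can produce associations for the three treatment flags and for cumulative GC dose with no true effect, and the incident/prevalent term does not prevent this. A null treatment-flag odds ratio of about 1.4 to 6 after that term is plausible under the assumed relapse risks, durations and uptake, none of which the documents supply. The distortion is small for rarely used drug classes and disappears if adjuncts start at diagnosis. The VAS scores are unsuitable as antecedent factors because of their timing. Only one exploratory secondary analysis is affected; the primary descriptive objective is not.

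**What to change.** Keep the logistic regression and amend SAP 5.5.2 and Tables 22–23 as follows:

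1. Force time since diagnosis (for example its log) into every model, including each model in Table 22, outside the screening and elimination steps.
2. Limit candidates to factors known at diagnosis. Drop the three treatment flags, cumulative GC dose and both VAS scores: 22 − 6 = 16. Forced time then supersedes the 6-week flag, leaving 15. Treatment before and for relapse stays described in Table 17.
3. Restriction to prevalent patients is optional; type of patient then drops out because it is constant.
4. Replace *effect* with *association* in both titles and label the model exploratory.
5. State that the on-treatment eligibility rule leaves a residual selection effect that time adjustment does not remove.

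The cost is SAP wording and one changed model, using data already planned. Because the protocol leaves the factors to the SAP, the protocol text can stay as it is. The price is that six post-diagnosis factors leave the model.
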